1 INTRODUCTION

This statistical analysis plan (SAP) describes the planned analysis and reporting for ZELTIQ Aesthetics protocol number 2022-01: A Multi-center, Prospective Study to Evaluate the Safety and Effectiveness of Multi-treatment Regimen with ZELTIQ Aesthetics, Inc. Rapid Acoustic Pulse (RAP)TM Device for the Improvement in the Appearance of Cellulite version Rev 01 dated 11 Jan 2023.

This SAP will be signed off, at a minimum, before the final database lock and contains detailed information to aid in the performance of the statistical analysis and reporting of the study data for use in the final clinical study report (CSR). This SAP is being written with due consideration of the recommendations outlined in the most recent International Conference on Harmonization (ICH) E9 Guideline entitled Guidance for Industry: Statistical Principles for Clinical Trials and the most recent ICH E3 Guideline and the Guidance for Industry: Structure and Content of Clinical Study.

2 STUDY OBJECTIVES

The purpose of this multi-site clinical study is to evaluate the safety and effectiveness of two (2) treatment sessions with the ZELTIQ Aesthetics, Inc. RAP device for the improvement in the appearance of cellulite.

2.1 PRIMARY EFFECTIVENESS OBJECTIVE

The primary effectiveness objective will demonstrate improvement in the appearance of cellulite as determined by correct identification of baseline vs 12-week post final treatment images.

2.2 SECONDARY OBJECTIVES

- Evaluate the safety of the RAP device for cellulite treatments after each treatment and at each follow-up visit
- Demonstrate improvement in the appearance of cellulite as determined by the study participants completing the Participant Satisfaction Survey (**Assessment 3 in the Protocol**) when comparing side-by-side baseline vs 12-week post final treatment images

3 STUDY DESIGN AND PROCEDURES

This is a non-significant risk, multi-center, multi-treatment (2 treatment sessions) prospective trial for safety, and effectiveness using ZELTIQ Aesthetics, Inc.'s RAP device for the improvement in the appearance of cellulite performed at up to four (4) clinical research sites in the United States.

Up to sixty (60) healthy participants between the age of 18-50 will be enrolled in this study.

Participants who sign the informed consent form and meet all the eligibility criteria will be enrolled in the study. Each participant will undergo acoustic rapid pulse (RAP) treatment sessions on both of their thighs and/or buttocks.

Total study duration is anticipated to be at or less than 60 weeks from the first participant visit to the last participant observation visit. A total of up to six (6) visits are planned for this study as shown in Table 1 of the protocol.

4 DETERMINATION OF SAMPLE SIZE

Up to sixty participants will be enrolled and treated in this study. The sample size is based on clinical and practical exploratory considerations and not on a formal statistical power calculation.

5 STUDY ASSESSMENTS AND SCALES

The following assessments are collected during the study.

5.1 PHOTOGRAPHY

Photographs will be taken under standardized lighting and equipment settings at baseline, and at 4-week post-first treatment, 12, 26, and 52-week post-final treatment visits. Photos taken as baseline will serve as control images for the assessment of post treatment photos. At the visit, the photographer will take multiple photos at each angle (posterior; posterior oblique left; posterior oblique right), but only the single best photo, as determined by the photographer, will be selected for each angle. Three blinded, independent photo reviewers will review the 12-week and baseline photos and identify which photos were taken at which visit, called an Independent Physician Review (IPR). Reviewers will be shown one image per participant that consists of three baseline photos at three different angles and three 12-week post-final treatment photos at the same three different angles. Participants will review the same image as the IPR for their self assessments.

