5.2 PARTICIPANT SATISFACTION SURVEY (ASSESSMENT 3 IN THE PROTOCOL)

The Participant Satisfaction Survey is used to grade participant-reported overall improvement of the treatment areas. The questionnaire is divided into two sections (participant's right or left side) of three questions graded on a 5-point Likert scale.

The six questions are scored from 1 to 5, where higher scores indicate higher agreement and more positive response:

- Strongly Agree = 5
- Agree = 4
- Neutral = 3
- Disagree = 2
- Strongly Disagree = 1

Scores of Agree = 4 or Strongly Agree = 5 to questions 1 and 4 will be considered an improved response for treatment effectiveness.

The Participant Satisfaction Survey will be administered at 4-week post-first treatment, 12, 26, and 52-week post-final treatment visits.

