6 GENERAL ANALYSIS AND REPORTING CONSIDERATIONS

Continuous data will be summarized using descriptive statistics: n, mean, standard deviation, median, minimum and maximum, Q1 and Q3, unless otherwise noted.

Categorical variables will be summarized using frequency counts and percentages. When count data are presented, the percentage for zero counts will be suppressed to draw attention to the non-zero counts. The denominator for all percentages will be the number of participants in that treatment group within the population of interest, unless otherwise noted.

The following conventions will be used throughout the study analysis:

- Baseline value is defined as the last valid measurement prior to the first RAP treatment.
- Change from baseline is defined as post-baseline value minus baseline value.
- If duplicate values are obtained at a given visit (e.g., repeated vital sign measurements), the last value will be used.

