6.2 STUDY HYPOTHESES

No formal hypothesis testing is planned.

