9 EFFECTIVENESS EVALUATION

9.1 EFFECTIVENESS ENDPOINT(S)

9.1.1 Primary Effectiveness Endpoint

Binary (yes/no) correct identification of baseline vs 12-week post-final treatment images of the treated body area(s) by at least two out of three blinded independent photo reviewers.

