9.2 EFFECTIVENESS ANALYSIS

9.2.1 Primary Effectiveness Analysis

The number and proportion of analyzable images that are correctly identified as baseline or 12-week post-final treatment by at least two out of three blinded IPRs will be summarized using the Evaluable population. The primary effectiveness objective will be met if $\geq 70\%$ of the baseline vs 12-week post-final treatment images of the treated body area(s) are correctly identified by at least two out of the three blinded IPRs.

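### The photographer's free choice of the best frame per angle leaves room for a visit-dependent choice in the primary endpoint that blinded reviewers cannot undo; no bias is shown

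*SAP*

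**What the plan says.** SAP 5.1 (Photography) standardises lighting and equipment. It has several frames taken at each of three angles, then states that "only the single best photo, as determined by the photographer, will be selected for each angle". It does not fix the number of frames or define what makes one best.

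Masking is described only for the three reviewers. Each participant is represented by one composite of three baseline and three 12-week frames, so the reviewers never see the rejected frames. The same section makes baseline the comparator: "Photos taken as baseline will serve as control images for the assessment of post treatment photos". It also ties the participants' ratings to the same composite: "Participants will review the same image as the IPR for their self assessments".

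SAP 9.1.1 defines the primary endpoint as correct identification "by at least two out of three blinded independent photo reviewers". SAP 9.2.1 declares the objective met when at least 70% of the images are "correctly identified by at least two out of the three blinded IPRs". SAP 6.2 adds: "No formal hypothesis testing is planned". The count against 70% is therefore the whole decision.

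**The concern.** The endpoint asks which photographs belong to which visit. Any consistent difference between the two sets of frames can help a reviewer answer, whether it comes from treatment or from the way frames were picked. The photographer picks before the reviewers see anything, so masking the reviewers protects the reading but not the selection.

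If a less flattering frame tended to be kept at baseline, or a more flattering one at 12 weeks, some composites would be read correctly with no true change in the skin. There is no concurrent untreated group in the readable text against which such an effect would show up. The planned supportive analysis (SAP 9.2.2) only repeats the primary analysis by subgroup, and none of the tables and listings in SAP 15 covers frame selection. What is at stake is whether meeting the 70% rule can be read as a treatment effect.

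**Working it through.** The plan gives no power, alpha or derived sample size, so there is no figure of its own to reproduce. The check asks how many composites frame choice would have to settle before the 70% rule loses its protection against chance.

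**Inputs from the documents**
- Up to 60 participants (SAP 4), one composite each (SAP 5.1), so n is at most 60.
- Success needs at least 70% (SAP 9.2.1): 0.70 × 60 = 42 composites.
- A composite counts as correct when at least two of three reviewers are right (SAP 9.1.1).

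**Assumptions, not in the documents**
- There is no true effect and no other visit cue.
- Frame choice settles k composites, all in the correct direction. A choice that favoured baseline would work the other way.
- The remaining n − k composites are guessed and are independent of each other.

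**Guessed composites.** With per-reviewer probability p and independent reviewers, the two-of-three probability is 3p² − 2p³. At p = 0.5 this is 3(0.25) − 2(0.125) = 0.5.

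**Chance that the rule is met.** P = P(Bin(n − k, 0.5) ≥ r − k), where r is the required count.

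For n = 60, r = 42:

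| k | Tail | Chance |
|---|---|---|
| 0 | Bin(60, 0.5) ≥ 42 | 0.13% |
| 6 | Bin(54, 0.5) ≥ 36 | 1.0% |
| 12 | Bin(48, 0.5) ≥ 30 | 5.6% |
| 23 | Bin(37, 0.5) ≥ 19 | 50% |

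The analysis is limited to analyzable images in the Evaluable population, so n may be below 60. For n = 40 as an assumed lower figure, r = 0.70 × 40 = 28:

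| k | Tail | Chance |
|---|---|---|
| 0 | Bin(40, 0.5) ≥ 28 | 0.8% |
| 6 | Bin(34, 0.5) ≥ 22 | 6.1% |
| 15 | Bin(25, 0.5) ≥ 13 | 50% |

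**Reading the tables.** If the same rule is applied in the same way at both visits, k = 0 and the first row of each table applies. At n = 60, frame choice would have to settle 12/60 = 20% of composites for the chance of a false success to reach about 5.6%. The documents do not say whether k is anything other than zero.

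A model-based estimate of k would need the number of frames per angle, how much frames differ from one another, reviewer error and the share of participants affected. The documents give none of these, so no such estimate is offered.

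**The case against.** The strongest reply is that SAP 5.1 states one rule for every visit. Applied alike at baseline and 12 weeks, it is neutral whether *best* means sharpest or best-looking. Every raised figure above therefore describes a departure from the rule, not its consequence. This stands, and it is why the point is about room for a visit-dependent choice and not about bias.

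The context also favours a technical meaning, since the section opens with standardised lighting and equipment and SAP 9.2.1 counts analyzable images. The protocol's procedure sections are largely redacted and may hold a photography standard. Both points stand: what can be said is that no criterion is readable, not that none exists.

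The photographer works at the visit and could hardly be masked to it. That is fair, and it is a reason to limit discretion by a written rule instead of asking for masking. The wording also suggests that the baseline frame is chosen at baseline, before any outcome is known. That narrows the opening but does not close it, because the 12-week frame is still chosen by someone likely to know the visit.

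A reader might go further in three ways that the documents do not support.
- **That frames are in fact chosen to flatter the follow-up.** A protocol exclusion criterion shows that the sponsor's team may take the photographs or be present. That is opportunity only; nothing shows such a choice.
- **That SAP 5.1 conflicts with SAP 6.** The general convention there reads "If duplicate values are obtained at a given visit (e.g., repeated vital sign measurements), the last value will be used". It concerns duplicate values, with vital signs as its example. Photographs have their own rule, and keeping the last frame could retain a poor one.
- **That the participant survey is inflated by a known amount.** It uses the same composite, but participants already know which photograph is which, and no size can be given.

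**Conclusion.** The point holds as an avoidable opening in the primary endpoint. A person not stated to be masked selects, on a criterion that cannot be read, the only frames that the reviewers see, and a bare count of their readings decides success. Masking the reviewers does not reach back to that selection.

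The size is unknown and no bias is shown. On the stated assumptions, the chance of meeting the rule without a true effect moves from 0.13% to 1.0%, 5.6% or 50% as frame choice settles 0, 6, 12 or 23 of 60 composites. These figures show how the rule responds; they are not evidence that any composite is affected. The wording is certain and the change is cheap, so the change is worth making even though the consequence is uncertain.

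**What to change.** In SAP 5.1, replace the photographer's choice of the single best photo with: *the first frame per angle that meets written technical criteria (focus, exposure, framing, pose), identical at baseline and follow-up and applied before any composite is shown to participants or reviewers; all frames are kept and the reason for each rejected frame is logged.* If the redacted protocol already holds such criteria, cite them in SAP 5.1.

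The SAP need only be signed before final database lock (SAP 1), so frames may already have been chosen. In that case keep the existing composites for both the primary and secondary endpoints, and do not change the rule for follow-up alone. Participants rate the same composite, and SAP 5.2 sets the timing: "The Participant Satisfaction Survey will be administered at 4-week post-first treatment, 12, 26, and 52-week post-final treatment visits". Choosing again after the 12-week rating would leave the two endpoints resting on different images. The CSR should then state who chose the frames, on what criteria, and, if so, that this person was not masked to visit.

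The cost is one sentence in the SAP and matching photography instructions. IRB submission is needed if data collection practice changes (Protocol, Regulatory and Ethical Compliance, item 6). If frames are already chosen, the cost is a short CSR statement. The downsides are that a technically second-best frame will occasionally be used, and that the photographer still judges which frames are acceptable.

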5.2 PARTICIPANT SATISFACTION SURVEY (ASSESSMENT 3 IN THE PROTOCOL)

The Participant Satisfaction Survey is used to grade participant-reported overall improvement of the treatment areas. The questionnaire is divided into two sections (participant's right or left side) of three questions graded on a 5-point Likert scale.

The six questions are scored from 1 to 5, where higher scores indicate higher agreement and more positive response:

- Strongly Agree = 5
- Agree = 4
- Neutral = 3
- Disagree = 2
- Strongly Disagree = 1

Scores of Agree = 4 or Strongly Agree = 5 to questions 1 and 4 will be considered an improved response for treatment effectiveness.

The Participant Satisfaction Survey will be administered at 4-week post-first treatment, 12, 26, and 52-week post-final treatment visits.

5.3 PROCEDURE TOLERABILITY QUESTIONNAIRE (ASSESSMENT 1 IN THE PROTOCOL)

The Procedure Tolerability Questionnaire is used to assess the comfort of the RAP treatment. It is divided into two sections (participant's right or left side) of three questions. The overall average pain per participant will be derived as the average of the responses to "The OVERALL pain score DURING the procedure?" and "The OVERALL pain score AFTER the procedure?" for all treatment sides. The overall average pain score cannot be computed if both questions are not answered. The individual responses are scored from 0 to 10, where higher scores indicated increased pain.

5.4 GLOBAL AESTHETIC IMPROVEMENT (GAIS) (ASSESSMENT 5 IN THE PROTOCOL)

The GAIS is completed by the Investigator to grade the overall improvement of each treatment area (thigh/buttock) by comparing baseline photos to post treatment photos at 4-week post-first treatment, 12, 26, and 52-week post-final treatment visits. The question is scored from 1 to 5, where higher scores indicate worse improvement:

- Very much improved = 1
- Much improved = 2
- Improved = 3
- No Change = 4
- Worse = 5

5.5 BODY-Q™ APPRAISAL OF CELLULITE (ASSESSMENT 4 IN THE PROTOCOL)

This self-administered 11-item scale measures how much someone is bothered by the appearance of cellulite. At each assessment, the raw scores for the set of items in a scale are added together to produce a total raw score. If less than 5 questions are missing, the within person mean for the completed items will be imputed for the missing items prior to computing a total raw score. The total raw score cannot be imputed if 5 or more questions are missing. Total raw scores are then converted to a Rasch transformed score in the range of 0 (worst) to 100 (best) using the Conversion Table. Both total raw scores and Rasch transformed scores will be captured in the CRF. The raw scores are scored from 1 to 4, where higher scores indicate the patient is less bothered:

Extremely bothered = 1

Moderately bothered = 2

A little bothered = 3

Not at all bothered = 4

Sum Score	Equivalent Rasch Transformed Score (0-100)
11	0

12	11
13	16
14	20
15	23
16	25
17	28
18	30
19	32
20	34
21	36
22	38
23	40
24	42
25	44
26	46
27	47
28	49
29	51
30	53
31	55
32	58
33	60
34	62
35	65
36	68
37	71
38	74
39	77
40	80
41	83
42	87
43	93
44	100

5.6 BODY-Q™ SATISFACTION WITH HIPS & OUTER THIGHS AND SATISFACTION WITH BUTTOCKS (ASSESSMENT 4 IN THE PROTOCOL)

Hips & Outer Thighs is a self-administered 5-item scale measuring satisfaction with the appearance of the hips and outer thighs. Buttocks is a self-administered 5-item scale measuring satisfaction with the appearance of the buttocks. At each assessment, for both scales, the raw scores for the set of items in a scale are added together to produce a total raw score. If less than 3 questions are missing, the within person mean for the completed items will be imputed for the missing items prior to computing a total raw score. The total raw score cannot be imputed if 3 or more questions are missing. Total raw scores are then converted to a Rasch transformed score in the range of 0 (worst) to 100 (best) using the Conversion Table. Both total raw scores and Rasch transformed scores will be captured in the CRF. The raw scores are scored from 1 to 4, where higher scores indicate the patient is more satisfied:

Very Dissatisfied = 1

Somewhat Dissatisfied = 2

Somewhat Satisfied = 3

Very Satisfied = 4

Sum Score	Equivalent Rasch Transformed Score (0-100)
5	0
6	13
7	19
8	24
9	29
10	33
11	38
12	43
13	48
14	54
15	63
16	73
17	80
18	86
19	93
20	100

5.7 FITZPATRICK SKIN TYPE SCALE (SCALE 2 IN THE PROTOCOL)

A participant's Fitzpatrick skin type is established by the Investigator at baseline using the six-category scale:

Skin Photo type	Typical Features	Tanning Ability
I	Pale white skin, blue/hazel eyes, blond/red hair	Always burns, does not tan
II	Fair skin, blue eyes	Burns easily, tans poorly
III	Darker white skin	Tans after initial burn
IV	Light brown skin	Burns minimally, tans easily
V	Brown skin	Rarely burns, always tans darkly
VI	Dark brown or black skin	Never burns, always tans darkly

6 GENERAL ANALYSIS AND REPORTING CONSIDERATIONS

Continuous data will be summarized using descriptive statistics: n, mean, standard deviation, median, minimum and maximum, Q1 and Q3, unless otherwise noted.

Categorical variables will be summarized using frequency counts and percentages. When count data are presented, the percentage for zero counts will be suppressed to draw attention to the non-zero counts. The denominator for all percentages will be the number of participants in that treatment group within the population of interest, unless otherwise noted.

The following conventions will be used throughout the study analysis:

- Baseline value is defined as the last valid measurement prior to the first RAP treatment.
- Change from baseline is defined as post-baseline value minus baseline value.
- If duplicate values are obtained at a given visit (e.g., repeated vital sign measurements), the last value will be used.

6.1 ADJUSTMENTS FOR COVARIATES

No adjustments for covariates are needed for this study.

6.2 STUDY HYPOTHESES

No formal hypothesis testing is planned.

6.3 HANDLING OF MISSING DATA

No imputation will be performed for missing data.

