6.4 ASSESSMENT TIME WINDOWING

No analysis visit windows will be utilized in this study and all safety and effectiveness assessment summaries will be based on the nominal protocol-specified assessment times.

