7.1.3 Evaluable

The Evaluable population consists of participants in the Safety population who completed the Resonic treatment plan (completed two treatment sessions) bilaterally for at least one location.

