9.1.3 Exploratory Effectiveness Endpoints

- The number of participants who have improvement in the appearance of cellulite as determined by the study participants selecting “Agree” or “Strongly Agree” as answers to the Participant Satisfaction Survey question(s) “In comparison to the pre-treatment photo, the final photograph of the treatment area appears improved.” on one or two sides at the 4-week post-first treatment, 12, 26, and 52-week post-final treatment visit.
- Binary (yes/no) improvement in the appearance of cellulite as determined by the study participants selecting “Agree” or “Strongly Agree” as answers to the Participant Satisfaction Survey question(s) “In comparison to the pre-treatment photo, the final photograph of the treatment area appears improved.” at the 4-week post-first treatment, 26, and 52-week post-final treatment visits by side (participant’s left or right).
- Overall average pain per participant derived as the average of the responses to “The OVERALL pain score DURING the procedure?” and “The OVERALL pain score AFTER the procedure?” for all treatment sides on the Procedure Tolerability Questionnaire at each treatment visit.
- GAIS as determined by the investigator at the 4-week post-first treatment, 12, 26, and 52-week post-final treatment visits.
- Actual and change from baseline in Body Q™ Appraisal of Cellulite, Satisfaction with Buttocks, and Satisfaction with Hip & Outer Thigh Rausch transformed total scores at the baseline, 4-week post-first treatment, 12, 26, and 52-week post-final treatment visits.

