9.2.4 Exploratory Effectiveness Analyses

All exploratory effectiveness analyses will be descriptive and summarized using the Evaluable population.

- Number and proportion of participants who have one or two sides improved at the 4-week post-first treatment, 12, 26, and 52-week post-final treatment visits via the Participant Satisfaction Survey.
- Number and proportion of sides that are improved at the 4-week post-first treatment, 26, and 52-week post-final treatment visits via the Participant Satisfaction Survey.
- Descriptive statistics for overall average pain per participant at the two treatment visits.
- Descriptive statistics for GAIS score at the 4-week post-first treatment, 12, 26, and 52-week post-final treatment visits via the investigator GAIS.
- Descriptive statistics for actual and change from baseline in Body Q™ Appraisal of Cellulite, Satisfaction with Buttocks, and Satisfaction with Hip & Outer Thigh Rausch transformed total scores at the 4-week post-first treatment, 12, 26, and 52-week post-final treatment visits.

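### The 12-, 26- and 52-week means of BODY-Q (and of GAIS, if it is averaged) can rest on different participants, so a trend across visits mixes true change with change in who attends

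*SAP*

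**What the plan says.** SAP 6.3 states "No imputation will be performed for missing data". SAP 5.5 and 5.6 make one exception. Missing items inside a BODY-Q questionnaire are replaced by the participant's own mean if fewer than 5 of 11 items, or fewer than 3 of 5, are missing. That rule does not fill a missed visit.

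SAP 9.1.3 lists "GAIS as determined by the investigator at the 4-week post-first treatment, 12, 26, and 52-week post-final treatment visits" and sets the same post-baseline visits for BODY-Q. For the analysis, SAP 9.2.4 says:

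- "All exploratory effectiveness analyses will be descriptive and summarized using the Evaluable population"
- "Descriptive statistics for actual and change from baseline in Body Q™ Appraisal of Cellulite" (and the two BODY-Q satisfaction scales)
- "Descriptive statistics for GAIS score at the 4-week post-first treatment, 12, 26, and 52-week post-final treatment visits via the investigator GAIS"

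SAP 6 gives the content of such a summary: "Continuous data will be summarized using descriptive statistics: n, mean, standard deviation, median, minimum and maximum", plus the quartiles. Visits are taken at face value, since under SAP 6.4 "all safety and effectiveness assessment summaries will be based on the nominal protocol-specified assessment times". SAP 7.1.3 defines Evaluable as "participants in the Safety population who completed the Resonic treatment plan (completed two treatment sessions) bilaterally for at least one location".

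The supportive analyses in SAP 9.2.2 are subgroups of the primary endpoint only. The titles of Tables 14.2.3 and 14.2.5.1 to 14.2.5.3 name no fixed cohort. The visible text has no paired 12-to-52-week change, no longitudinal model and no sensitivity analysis for missed visits. Much of the protocol is blacked out, so a rule there cannot be excluded.

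**The concern.** Each visit's mean is taken over the Evaluable participants who have data at that visit. BODY-Q change is paired with each participant's own baseline, so the result within one visit is sound for the people seen. The step from 12 to 26 to 52 weeks is not paired. The protocol lets participants withdraw at any time, and nothing in the Evaluable definition keeps the later visits to the same people.

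A reader of Tables 14.2.5.1 to 14.2.5.3 will naturally read down the visits to see whether the effect holds. With one treated group, no comparator arm would show the same attrition pattern. What is at stake is any statement in the study report about how the effect behaves after 12 weeks.

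**Working it through.** The plan states no SD, dropout rate or expected BODY-Q change, so there is no figure to reproduce. All inputs below are assumptions, apart from the limit of 60 participants in SAP 4.

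**1. Size of a purely compositional shift.** Suppose every participant's BODY-Q change is the same at 52 weeks as at 12. Let a fraction d be lost, and let rho be the correlation between the change and a normally distributed tendency to leave (positive when the less improved leave). Then

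false shift = rho × SD × φ(z_d) / (1 − d).

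The factor φ(z_d)/(1 − d) is 0.195, 0.350 and 0.497 for d = 10%, 20% and 30%. With SD = 20 points:

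| Loss | Random (rho = 0) | rho = 0.5 | rho = 1 (exactly the least improved leave) |
|---|---|---|---|
| 10% | 0 | 0.5 × 20 × 0.195 = 1.95 | 20 × 0.195 = 3.9 |
| 20% | 0 | 0.5 × 20 × 0.350 = 3.5 | 20 × 0.350 = 7.0 |
| 30% | 0 | 0.5 × 20 × 0.497 = 5.0 | 20 × 0.497 = 9.9 |

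A second model made dropout a logistic function of the 12-week change, with odds ratios of 1.5 to 3 per SD. It gave 0.04 to 0.27 SD over the same loss rates, which is 0.8 to 5.4 points at SD 20.

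**2. Direction, in a two-group example.** Take 60 participants at 12 weeks: 30 responders (BODY-Q change +20, GAIS 2) and 30 non-responders (change 0, GAIS 4). The 12-week means are 10.0 and 3.00.

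- *Non-responders lose 40%, responders 10%, nobody changes.* Remaining: 18 and 27. BODY-Q change = 27 × 20 / 45 = 12.0; GAIS = (27 × 2 + 18 × 4) / 45 = 2.80. Both show growth that did not happen.
- *Loss reversed (10% and 40%).* BODY-Q change = 18 × 20 / 45 = 8.0; GAIS = (18 × 2 + 27 × 4) / 45 = 3.20. Both show a decline that did not happen.
- *Equal loss.* The means stay at 10.0 and 3.00.
- *Non-responders lose 40%, responders 10%, and responders fade to +16.* The true mean for all 60 is 30 × 16 / 60 = 8.0. The displayed mean is 27 × 16 / 45 = 9.6. A real fall of 2.0 appears as a fall of 0.4.

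**3. What the added rows would show**, with 40% and 10% loss. The 45 participants seen at both visits have 12.0 at 12 weeks and 12.0 at 52 weeks if nobody changes, so the false growth disappears. If responders fade, the same 45 go from 12.0 to 9.6, and the fade is visible. The 12-week split gives 12.0 for the 45 who stay and 3 × 20 / 15 = 4.0 for the 15 who leave. This explains the whole shift: 0.25 × (12.0 − 4.0) = 2.0. The level for the 45 is still 12.0 against 10.0 for all 60, so selection in the level remains.

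**The case against.** **The stakes are limited, and that stands.** BODY-Q and GAIS are exploratory and descriptive. No hypothesis is tested (SAP 6.2), and the only success rule concerns the 12-week photographs (SAP 9.2.1). A reader might assume that the 26- and 52-week visits exist to prove durability. The visible text states no durability objective or threshold: the effectiveness objectives in SAP 2.1 and 2.2 are set at 12 weeks, and safety is followed at every visit.

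**Some mitigation is already planned.** Each summary shows n. SAP 7.2 reports 12-week completion, study completion and reasons for withdrawal. Listings 16.2.6.4 and 16.2.6.5.1 to 16.2.6.5.3 would let a determined reader follow individuals. So it would be too strong to say that the data cannot separate the two explanations. However, counts show how many were lost, and no planned table shows whether those lost had done worse at 12 weeks.

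**Two stronger readings fail.** A reader might infer that dropout creates a false lasting benefit when nobody has changed. If nobody has changed since 12 weeks, the benefit has in fact lasted and only apparent growth is false; a false picture of durability needs a real fade that dropout hides. A reader might also infer that selective loss always flatters the result. The direction depends on who leaves, which the documents do not tell us.

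**GAIS is less certain.** Reading its summary as a mean is an inference, supported by SAP 9.2.4 asking for numbers and proportions for the survey items but descriptive statistics for the GAIS score. If Table 14.2.3 gives percentages, the default denominator in SAP 6 is the whole population. Dropout would then lower the percentage improved (in the example from 30/60 = 50% to 27/60 = 45%).

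**Conclusion.** The point holds as a low-priority reporting gap. For BODY-Q, and for GAIS if it is averaged, comparisons across 12, 26 and 52 weeks confound change within people with change in who is observed. The error can be false growth, a hidden fade or a false decline.

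Under the assumed SD of 20 and loss of 10% to 30%, the shift runs from nothing (random loss) through about 2 to 5 points (moderate selection). The 3.9 to 9.9 points are a ceiling that needs perfectly ordered dropout, and should not be quoted as the expected bias. The mechanism follows from the SAP; the size rests wholly on assumed inputs.

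**What to change.** In SAP 9.2.4 and Tables 14.2.5.1 to 14.2.5.3 (and 14.2.3 if GAIS is summarised as a mean), keep the all-available rows and add:

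1. the same statistics at 12, 26 and 52 weeks, with the paired 12-to-52-week change, for participants assessed at all three visits;
2. the 12-week result split by whether the 52-week assessment is present.

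State in the SAP that any comment on durability will rest on these rows, and that the fixed cohort removes the false trend but not selection in the level. State also whether Table 14.2.3 reports means or percentages, and with what denominator. Reword 6.3 so that it refers to missed visits and points to the item rules in 5.5 and 5.6.

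A descriptive repeated-measures model for BODY-Q is optional. It needs no hypothesis test, but if baseline score is included, SAP 6.1, which rules out covariate adjustment, must be amended.

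The cost is SAP wording and a few table rows from data already collected. The drawback is a smaller n in the added rows, which sit beside the planned ones.
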